**Topical Antibiotic Irrigation (Gentamicin) in Prophylaxis of Midfacial Fracture
Surgical Wounds**

NCT 03483363

Version Date: 05/08/2020

Protocol Title:	Topical Antibiotic Irrigation (Gentamicin) in Prophylaxis of Midfacial Fracture Surgical Wounds
Principal Investigators:	[name]
Co-Investigators:	[name], [name], [name], [name]
Faculty Advisor:	[name], [name], [name]
Population:	Adult Patients admitted to Memorial Hermann Hospital (MHH) for treatment of Midfacial fractures
Number of Sites:	Memorial Hermann Hospital
Study Duration:	Prospective trial, 4 years
Subject Duration:	Associated hospital stays, Follow up to eight weeks postoperatively

General Information

The purpose of this study is to evaluate the use of topical antibiotic irrigation (Gentamicin) and its ability to reduce surgical site infections in midfacial fracture surgery compared to sterile normal saline (NS).

Background Information

The Centers for Disease Control and Prevention estimates that 16 million surgical procedures were performed in acute care hospitals in the United States in 2010 (CDC). A recent study found that surgical site infections (SSIs) accounted for roughly 31% of all hospital acquired infections (HAIs) (Magill). The overall infection rate for traumatic midfacial fracture is about 9% (Lauder). Current regimens applied for prevention of SSIs include: preoperative antiseptic preparation and systemic parenteral antibiotic prophylaxis, intraoperative aseptic techniques, and postoperative incision care (Mangram).

Intraoperative topical antibiotic irrigation intraoperatively is becoming more prevalent, supplementing the recommended use of intravenous prophylactic administration of antibiotics prior to surgery (Andreasen). Typical irrigation agents include sterile saline, Gentamicin, chlorhexidine gluconate, betadine, Bacitracin, and hydrogen peroxide. The majority of prospective references reviewed were limited to orthopedic, abdominal, ocular, breast, dermatologic, and cardiothoracic surgeries with a significant lack of sources referencing maxillofacial surgeries (McHugh). The available reports on the use of topical antibiotic irrigation in prophylaxis of facial surgical wounds is insufficient.

Objectives

- Does the use of topical antibiotic irrigation (Gentamicin) reduce surgical site infections in midfacial fracture surgery compared to sterile NS?

Study Design

- Prospective randomized trial: All groups will receive standard parenteral (IV) prophylactic antibiotic. In the control group, the fractures will be irrigated with sterile normal saline prior to closure. In the trial group, the fractures will be irrigated with Gentamicin topical antibiotic

(80mg diluted in 1L 0.9% NS) prior to closure. Patients will not receive postoperative oral antibiotics.

- Double blinded: Intraoperative irrigation will be concealed (saline vs Gentamicin) to the patient and the surgeon.
- Expected duration of study is about 4 years and subject participation is expected to be about 200.
- The primary outcome to be measured is the rate of surgical site infections. The main investigator ([name]) will determine SSI (evidence of infection: persistent swelling, fever, recurrent swelling, erythema, and purulent discharge). Statistical analysis plan will be multivariate: SSI, use of Gentamicin, type of fracture, past medical history, social history, days before surgery.
- Assessment of efficacy.
- Assessment of safety.

Gentamicin information – Topical use

- Please see separate package insert document for more detailed information
- A topical irrigation solution may be compounded by dissolving appropriate amount of Gentamicin injection or Gentamicin compounding powder in 0.9% Sodium Chloride injection or sterile water for injection for a final concentration of 0.08mg/mL.
- This drug is contraindicated in those individuals with a history of previous hypersensitivity or allergic reaction to it
- Dosage form: 8mg/Vial, injection
- Maximum dosage: 5 mg/kg/day IV/IM is FDA-approved maximum. There is no maximum dose stated for ophthalmic or topical administration.
- There is no premixed solution. The Gentamicin is obtained at the hospital pharmacy and is mixed with 0.9% normal saline in the operating room by the scrub tech under sterile condition with nurse practitioner supervision ([name]) in order to maintain the blind. 80mg will be used per patient.

Study Population

- Inclusion: All patients 18 years of age and older who are planned for open reduction internal fixation of midfacial fractures as part of standard of care
- Exclusion: Infected surgical sites, allergies to Gentamicin
- Recruitment: Will recruit all patients who are admitted to Memorial Hermann hospital at Texas Medical Center

Study Procedures

- Expected number of visits will be about 5. First visit will be for evaluation in emergency department. Second visit will be for surgery. Also, patient will be monitored in the hospital postoperatively and will be seen for follow up in clinic.
- Every case included will be randomized based on lottery system for intraoperative sterile saline vs Gentamicin irrigation
- Every administered agent will not be known to patient or surgeon
- Patient will be then followed and monitored as per standard of care (inpatient monitoring, clinic follow up after discharge, last follow up at 8 weeks)
- The following will be considered evidence of infection: persistent swelling, fever, recurrent swelling, erythema, and purulent discharge

- Patient information will be gathered to evaluate the type of surgery, medical history of patient, research intervention of irrigation, types of antibiotics used, inpatient recovery, and follow up care. The information will be recorded an encrypted separate electronic document to ensure protection of patient information: secureshare.uth.tmc.edu

Data and Safety Monitoring

- Adverse events are not expected
- Data will be collected and kept by designated research assistants, [name] and [name].
- Data will be kept on the secured website: secureshare.uth.tmc.edu
- Interpretation of all information and results to be calculated at the conclusion of the last follow up of the last case included in the study to reduce bias
- At the conclusion of the study, data kept will have no patient information but still will be stored in the secured location

Statistics

- The aim of this study is to mainly compare the statistical outcomes between each group. Once the data tabulation is completed, other statistical analysis may be pursued after consultation with the statistician in UT Health.
- Prior to data requisition, UTHealth statisticians, [name] and [name], were consulted for sample size calculation assistance.
- Given the prevalence of surgical wound infection in our target population is 9%, with a sample size of 100 per group (200 total), a type 1 error rate of 0.05 and a type 2 error rate of .80 (80% power), we will be able to detect a reduction of 9 percentage points, from 10% in the saline group to 1% in the topical antibiotic group.

Ethics

- IRB approval will be sought from CPHS. Start of project will be conducted only after all permissions and approval are granted. Chart reviews and data collection will be conducted only after all permissions and approval are granted
- Consent will be obtained from each patient using standard consent forms for the specific surgery. A separate research consent form will be completed by each patient discussing the research study specifically.
- Once IRB approval is granted, additional application to the respective hospital will be submitted individually to the respective research office and the offices of the respective chiefs of staff

Data handling and record keeping

- Data will be collected using medical record numbers avoiding any specific patient's identifiers
- Data will be secured in secureshare.uth.tmc.edu or similar UT Health approved storage media

Quality control and assurance

- Data collections will be performed by research assistants

Publication Plan

- Data and conclusion will be shared internally for quality improvement
- Data will be also shared in local and national professional meetings
- Future publications in professional journals

Attachments

- See specific data collection outline below

Data Collection

MRN		
Age		
Gender		
PMHx		
Medications		
Allergies		
Social history		
Injuries		
Type of fracture		
Days before Surgery		
Gentamicin		
No Gentamicin		
Post-op Hospital Course		
Follow up #1		
Follow up #2		
Infection		
No Infection		
Other Complications		

References

2. (CDC) "Surgical Site Infection (SSI) Event." *Centers for Disease Control*, Jan. 2017, Web: <https://www.cdc.gov/nhsn/pdfs/pscmanual/9pscscurrent.pdf>.

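### The investigator who decides surgical site infection and the staff who record it are not stated to be blinded, and the data sheet lists the arm in plain words beside the outcome

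*Combined protocol and SAP*

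**What the plan says.** - **Who decides the outcome.** Study Design makes the SSI rate the primary outcome and gives the decision to one person. The main investigator "will determine SSI (evidence of infection: persistent swelling, fever, recurrent swelling, erythema, and purulent discharge". Study Procedures repeats the five signs. Neither section sets a threshold or a required number of signs, and no second assessor is described.
- **Who is blinded.** Study Design defines double blinding in these words: "Intraoperative irrigation will be concealed (saline vs Gentamicin) to the patient and the surgeon". Study Procedures names the same two parties: "Every administered agent will not be known to patient or surgeon".
- **Who knows the arm.** Under the heading on topical gentamicin, the drug is "mixed with 0.9% normal saline in the operating room by the scrub tech under sterile condition with nurse practitioner supervision", with the aim of keeping the blind.
- **Who handles the data.** Data and Safety Monitoring says: "Data will be collected and kept by designated research assistants". Their blinding is not mentioned.
- **What is recorded together.** Study Procedures lists the information to be gathered, including "research intervention of irrigation, types of antibiotics used, inpatient recovery, and follow up care. The information will be recorded an encrypted separate electronic document". The Data Collection outline under Attachments, identified by medical record number, has rows for Gentamicin and "No Gentamicin". Below them are the post-operative course, two follow-ups, and infection or no infection. No coded arm and no separate allocation list is described.
- **Other bias control.** Data and Safety Monitoring defers interpretation and results until the last patient's last follow-up.

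**The concern.** The blind is defined for the two people at the operation. It is not extended to the person whose judgement is the primary outcome or to the staff who write that judgement down. Fever and purulent discharge are fairly objective. Whether swelling is persistent, or erythema is more than expected after facial surgery, is a matter of judgement. An assessor or recorder who knows that a patient had gentamicin may read a borderline sign as healing, and may read the same sign after saline as infection.

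A form completed as laid out would put the arm in view of whoever enters the outcome. SSI is the only primary outcome and few events are expected, so a small lean in borderline calls could change the trial's conclusion.

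**Working it through.** **1. The plan's own figure.** Statistics gives 100 per group, type 1 error 0.05, 80% power, and 10% vs 1%. With the usual two-sided formula (pooled variance under the null, no continuity correction):

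n = [1.960·√(2·0.055·0.945) + 0.842·√(0.10·0.90 + 0.01·0.99)]² / 0.09²

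This gives (0.632 + 0.266)² / 0.0081 ≈ 99.5, so 100 per group, with 80.2% power. The figure reproduces. Blinding the assessor does not alter it.

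**2. The text set side by side.**

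| Role | Knows or could learn the arm? | Stated to be blinded? |
|---|---|---|
| Patient | Concealed | Yes, twice |
| Surgeon | Concealed | Yes, twice |
| Scrub tech, supervising nurse practitioner | Yes, through preparation | Not applicable |
| Main investigator (decides SSI) | Possible through the record | No |
| Research assistants (collect and keep data) | Possible through the record | No |

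The documents do not say who may open the record, when the arm row is completed, or whether the main investigator also operates.

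**3. Expected events.** At the plan's 9%, 100 × 0.09 = 9 infections per group. One changed call is 1/9 = 11% of an arm's true events, and two are 2/9 = 22%.

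**4. Effect of a lean on the false-positive rate.** These are assumptions, not figures from the plan: the true SSI rate is 9% in both arms, and a lean of one call means a one-percentage-point change in that arm's recorded rate. The plan names no test and no sidedness, so I used a two-sided 0.05 level and show both common tests. The rejection rate is the sum, over all pairs of counts (x, y) that reach significance, of Bin(x; 100, p_saline) × Bin(y; 100, p_gentamicin).

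| Recorded rates, saline vs gentamicin | Any false positive: chi-square (Fisher) | Favouring gentamicin: chi-square (Fisher) |
|---|---|---|
| 9% vs 9%, no lean | 5.2% (2.8%) | 2.6% (1.4%) |
| 9% vs 8%, one call in one arm | 5.9% (3.2%) | 4.5% (2.5%) |
| 10% vs 8%, one call per arm | 8.0% (4.7%) | 7.3% (4.3%) |
| 11% vs 7%, two calls per arm | 17.0% (11.2%) | 16.8% (11.1%) |

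Chi-square is uncorrected.

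**5. Sensitivity of the hoped-for result.** With 100 per group:

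| Infections, saline vs gentamicin | Chi-square p | Fisher p |
|---|---|---|
| 10 vs 1 | 0.005 | 0.010 |
| 10 vs 2 | 0.017 | 0.033 |
| 10 vs 3 | 0.045 | 0.082 |

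The planned result survives one changed call. After two, significance depends on the test.

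**The case against.** The strongest reply is that this is an omission and that no unblinding has been shown. Names are removed from the public text. If the main investigator is also the operating surgeon, the existing concealment covers that person during the operation. Judging and recording are separate roles, and nothing says the investigator consults the data sheet before deciding. The Data Collection page is an outline of row labels without rules on timing or access, so treating it as the working form is an inference. The plan also shows intent to protect the blind: the mixing is arranged for that purpose, and interpretation waits until the last follow-up.

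Most of this limits how strongly the point can be put. It does not remove the point:

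- An investigator who operates could still learn the arm from the shared record, and the research assistants would remain uncovered.
- Deferring interpretation controls when results are read. It does not control who knows the arm when SSI is judged, up to eight weeks after surgery.
- Concealed mixing protects the operation but not the follow-up record.

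The numerical objection partly stands. A lean of one call in one arm hardly matters. With one call per arm, Fisher's test stays under 5% overall, although false positives favouring gentamicin triple from 1.4% to 4.3%. A marked rise needs about two calls in each arm, all in the same direction.

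**Conclusion.** The concern holds, and the plan should be changed. A trial described as double blinded does not extend the blind to the person who decides its primary outcome or to those who record it, and its data outline places the uncoded arm with that outcome. This is an open route to bias, not evidence that bias occurs.

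The possible size runs from negligible to a false-positive rate of about 17% (chi-square) or 11% (Fisher). That range rests on no true effect, 9% SSI, 100 per arm, and an assumed lean of up to two calls per arm by someone who knows the allocation. The documents give no basis for estimating the actual lean. Confidence is moderate because access to the record, the timing of the arm entry, and whether the investigator is the surgeon are all unstated.

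**What to change.** 1. Take the two gentamicin rows off the patient data sheet, and take the irrigation arm out of the electronic document that holds follow-up. Add a study number to the sheet.
2. Hold the allocation by study number in a separate restricted list until SSI status is final for every patient. The holder should be someone who already knows the arm from preparing the irrigation and who takes no part in assessing or recording SSI.
3. In Study Design and Study Procedures, extend the blinding statement to four parties: the patient, the surgeon, the investigator who determines SSI, and the research assistants who record outcomes.
4. Merge the list with the outcome data only after the last follow-up of the last patient. The plan already starts its analysis then, and the multivariate analysis does not need the arm sooner.

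The cost is one form split in two and one statement reworded in two places. Sample size, visits and staffing do not change. Keeping the list becomes a task for someone who prepares the irrigation. If the research assistants currently run the lottery or fill in the arm, which the documents do not say, that duty has to move. If the assessor is already blinded in practice, the sponsor need only write that down and separate the form.

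### The primary SSI analysis has no named test, sidedness or stated role for the multivariate model, and about 11 expected infections are too few for that model fitted in the ordinary way

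*Combined protocol and SAP*

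**What the plan says.** Under Study Design the outcome is set out as follows: "The primary outcome to be measured is the rate of surgical site infections". The analysis follows in the same bullet: "Statistical analysis plan will be multivariate: SSI, use of Gentamicin, type of fracture, past medical history, social history, days before surgery". This is a list of variables. It gives no model type, test, effect measure or covariate coding.

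The Statistics section opens with a broader aim: "The aim of this study is to mainly compare the statistical outcomes between each group". It then leaves further work open: "Once the data tabulation is completed, other statistical analysis may be pursued after consultation with the statistician in UT Health". The sample-size bullet gives 100 per group, "a type 1 error rate of 0.05" and 80% power for a fall "from 10% in the saline group to 1% in the topical antibiotic group". The same bullet gives the infection prevalence in the target population as 9%. Sidedness is not stated.

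No section says whether the group comparison or the multivariate model is the primary analysis.

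**The concern.** Two different analyses are in play. The sentence attached to the primary outcome describes a multivariate model, and the sample size fits a plain comparison of two proportions. Neither is named as primary, and neither comes with a test.

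Two things are at stake. First, the test could be chosen after the counts are known, and with so few infections that choice sometimes decides which side of 0.05 the result falls on. Second, the listed model has very little information to work with. If gentamicin performs as the design assumes, an arm with no infections is a realistic result, and the most familiar way of fitting the model breaks down there. The plan has no rule for that case.

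**Working it through.** **Inputs.** From Statistics: 100 per group, alpha 0.05, rates of 10% and 1%, and the 9% prevalence. From Study Design: gentamicin plus four covariates (fracture type, medical history, social history, days before surgery). The true gentamicin rates of 2% and 3% are my assumptions, used to show a range.

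**1. The plan's own figure.** Two-sided 0.05, pooled variance under the null, no continuity correction:
- Mean rate = (0.10 + 0.01)/2 = 0.055.
- Null SE = √(2 × 0.055 × 0.945/100) = 0.03224.
- Alternative SE = √((0.10 × 0.90 + 0.01 × 0.99)/100) = 0.03161.
- Power = Φ((0.09 − 1.96 × 0.03224)/0.03161) = Φ(0.848) = 80.2%.

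So 100 per group is reproduced. A one-sided test with continuity correction also gives 100 per group (80.3%), so the sample size alone does not settle the test or its sidedness.

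**2. Information for the model.** Expected infections = 100 × 0.10 + 100 × 0.01 = 11. Coefficients are at least 1 + 4 = 5, and more if fracture type or history has several levels. That is at most 11/5 = 2.2 infections per coefficient.

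**3. Chance of no gentamicin infections.** This is (1 − rate)^100:
- 1%: 0.99^100 = 37%.
- 2%: 0.98^100 = 13%.
- 3%: 0.97^100 = 5%.

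With a zero cell, maximum-likelihood logistic regression has no finite odds ratio. For 10 vs 0 the chi-square p is 0.0012 and the Wald p is near 1.

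**4. Power by test.** Exact binomial enumeration of all unadjusted 2×2 tables, two-sided, p < 0.05, with the Wald p set to 1 when a cell is zero:

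| True rates | Chi-square | Fisher | Wald (assumed) |
|---|---|---|---|
| 10% vs 1% | 85.4% | 76.9% | 44.9% |
| 10% vs 2% | 69.1% | 58.7% | 50.9% |
| 10% vs 3% | 53.0% | 42.4% | 43.2% |
| 9% vs 1% | 78.8% | 67.7% | 37.6% |

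**5. Chi-square against Fisher.** The share of trials in which the two fall on opposite sides of 0.05 is 8.5% at 10% vs 1%, 10.4% at 10% vs 2%, 10.7% at 10% vs 3%, and 11.0% at 9% vs 1%.

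Single tables, saline vs gentamicin infections:
- 10 vs 1 (expected): chi-square 0.005, Fisher 0.010, Wald 0.024. All are below 0.05.
- 9 vs 2 (the same 11 infections): chi-square 0.030, Fisher 0.058.
- 7 vs 1: chi-square 0.030, Fisher 0.065.

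**6. Type 1 error.** With 9% in both groups, chi-square rejects in 5.2% of trials and Fisher in 2.8%. Over common rates from 1% to 15%, chi-square stays at or below 5.2%.

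**The case against.** The best defence is that the Statistics section makes the group comparison the main aim and calls anything later other analysis. On that reading the model is only supportive, and a routine test would be used. Interpretation is also held back until the last follow-up, to limit bias. This is a fair reading and it narrows the doubt about the model's role. It still names no test and gives no sidedness, and the chi-square and Fisher disagreement arises within that very reading. Timing the interpretation does not fix the method.

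Several limits stand:
- Every figure here is for an unadjusted 2×2 table. The effect of covariate choice and coding, which may be the larger freedom, is not quantified.
- Some chi-square and Fisher disagreement occurs at any event rate. It is 7.4% at 20% vs 10%, so small counts are only part of the cause.
- If any single listed sign counts as an SSI, which the plan does not settle, rates would be higher and zero cells rarer.

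A reader might infer that the listed model would lose most of its power when gentamicin works well. The documents do not support that. They name neither logistic regression nor Wald p-values, and even on that assumption the loss is about half at a true rate of 1% and much less at 2% or 3%. A reader might also add the likelihood-ratio test, which raises the disagreement at the design rates to 13%. That test rejects 9.5% of the time under the null at a common rate of 2%, so it is a poor candidate here, and 8.5% is the fairer figure.

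**Conclusion.** The gap is real and should be fixed. The plan names no primary test, no sidedness and no role for the model, and the analysis it lists does not match the comparison on which the trial was sized.

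For the simple comparison, the choice between two routine tests decides significance in about 1 trial in 12 at the design rates, and 1 in 9 at 9% vs 1%. This is a minority of trials, and the choice of test does not alter the observed direction of effect. It would be wrong to infer that the tests conflict at the expected result, since all of them are below 0.05 at 10 vs 1.

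For the listed model, the zero-cell problem has a 37% chance at the design rate of 1%, falling to 13% at 2% and 5% at 3%. The power of about 45% is conditional on ordinary logistic regression with Wald p-values, and the verdict does not depend on it. The figures assume 100 analysed patients per group and independent binary outcomes.

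**What to change.** State that the primary analysis is the unadjusted two-sided comparison of SSI proportions by randomised group, using one named test. The uncorrected chi-square test at 0.05 is consistent with the stated sample size. Report the risk difference with a 95% score-type interval, for example Miettinen-Nurminen, which stays finite with a zero cell (10 vs 0 gives 5.5 to 17.5 points).

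State the power that goes with the chosen test. Exact chi-square power is 85.4% at 10% vs 1% and 78.8% at 9% vs 1%. If Fisher's exact test is chosen, restate power as about 77% (68% at 9% vs 1%). Another score or exact method would also close the gap if it is named in advance.

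Make the multivariable model secondary. Limit it to few covariates, fix their coding before unblinding, and use a method that tolerates a zero cell, such as Firth penalised likelihood with profile-likelihood intervals.

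The cost is wording only, with no extra patients or data. The primary test gives up any modest gain from covariate adjustment. Chi-square is approximate with sparse counts, though its null rejection rate is only about 5.2% at 9% in both groups.

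### Must the plan fix in advance how patients without an 8-week assessment count in the infection rate, and allow for their loss in the power statement?

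*Combined protocol and SAP*

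**What the plan says.** Under Study Design the endpoint is given in one sentence, without a time point or denominator: "The primary outcome to be measured is the rate of surgical site infections". The time frame appears elsewhere. The protocol summary lists, under Subject Duration, "Follow up to eight weeks postoperatively", and Study Procedures adds: "Patient will be then followed and monitored as per standard of care (inpatient monitoring, clinic follow up after discharge, last follow up at 8 weeks".

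Signs that count as infection are listed in Study Procedures: "The following will be considered evidence of infection: persistent swelling, fever, recurrent swelling, erythema, and purulent discharge". The model is sketched under Study Design: "Statistical analysis plan will be multivariate: SSI, use of Gentamicin, type of fracture, past medical history, social history, days before surgery".

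The Statistics section bases its power on 100 patients per group, 200 in total. Study Design expects the same number: "subject participation is expected to be about 200". Statisticians appear twice in the Statistics section. Beforehand they "were consulted for sample size calculation assistance". Later, "Once the data tabulation is completed, other statistical analysis may be pursued after consultation with the statistician in UT Health".

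The Data Collection outline has rows for the hospital course, two follow-up visits, infection and no infection. It has no entry for a patient whose status is unknown. No section defines an analysis population, a rule for missing outcomes or an allowance for loss.

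**The concern.** Follow-up by routine clinic visits usually loses some patients. Two of the five listed signs, persistent and recurrent swelling, need more than one look, so a patient last seen early with no infection noted may not be a true negative. Three rules are in common use:

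- **A.** Analyse only patients assessed at 8 weeks.
- **B.** Analyse patients with known 8-week status or an infection recorded earlier.
- **C.** Analyse everyone, counting the unassessed as uninfected.

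At the planned rates only about 11 infections are expected (100 × 10% + 100 × 1%), so moving a few patients can move the p-value across 0.05. If the rule were chosen after seeing infections by arm, the type I error could rise. With enrolment equal to the calculated sample size, any exclusion would also cut the number analysed below 100 per group. What is at stake is the credibility of a borderline result and the meaning of the 80% figure.

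**Working it through.** **Inputs.** From the Statistics section: 10% versus 1%, type 1 error 0.05, 100 per group, 80% power. The text attaches 0.80 to the type 2 error, but its parenthesis makes the meaning clear. The test and its sidedness are not stated; two-sided is assumed because it reproduces the plan. Loss d is not in the documents, so 10%, 20% and 30% are assumed. Loss is taken as equal in both arms and unrelated to infection, with half of the lost patients' infections seen before loss.

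**1. The plan's figure.** Pooled mean rate (0.10 + 0.01)/2 = 0.055.

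Power = Φ{[0.09√n − 1.96√(2 × 0.055 × 0.945)] / √(0.10 × 0.90 + 0.01 × 0.99)} = Φ{[0.09√n − 0.632] / 0.316}.

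At n = 100: (0.900 − 0.632)/0.316 = 0.848, so power is 80.2%. The plan's statement reproduces with no term for loss.

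**2. Fewer analysed (rule A).** The same formula gives 78.1% at 95 per group, 75.9% at 90 and 70.8% at 80. Exact power at 100, 90 and 80 is 85.4%, 80.9% and 75.5% by pooled z, or 76.9%, 70.0% and 61.6% by Fisher's test. The unnamed test therefore moves power by 85.4 − 76.9 = 8.5 points at full enrolment, about as much as 20% loss does by the formula (80.2 − 70.8 = 9.4).

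**3. Power when recorded infections are kept (rule B).** Simulation with 100 randomised per arm gives 84.6%, 82.5% and 79.9% (pooled z) at 10%, 20% and 30% loss, or about 77.7%, 74.8% and 71.4% (Fisher). So 80% at 100 evaluable patients per group describes rule A and does not carry over to rule B.

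**4. Expected difference in percentage points; the true value is 9.0.** At 20% loss:

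- A: 10 − 1 = 9.0.
- B: (8 + 1)/(80 + 1) − (0.8 + 0.1)/(80 + 0.1) = 11.11 − 1.12 = 9.99.
- C: 9.0 − 0.9 = 8.10.

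| Loss | A | B | C |
|---|---|---|---|
| 10% | 9.0 | 9.44 | 8.55 |
| 20% | 9.0 | 9.99 | 8.10 |
| 30% | 9.0 | 10.68 | 7.65 |

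In this model A is unbiased but discards observed infections, B overstates and C understates.

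**5. How often the rules disagree on p < 0.05** (10% versus 1%; loss 10%, 20%, 30%). All three rules: 4.9%, 9.1%, 14.3% (pooled z) or 7.1%, 12.0%, 17.4% (Fisher). B against C only: 2.1%, 3.0%, 4.0% (pooled z) or about 4.0%, 4.9%, 5.1% (Fisher). Much of the disagreement comes from A, and nothing in the Study Design endpoint makes an infection depend on attending the 8-week visit.

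**6. Type I error (9% in both arms).** Any one rule: 4.9% to 5.2% (pooled z) or 2.7% to 3.6% (Fisher). Taking whichever of the three is significant: 6.3%, 7.0%, 7.6% (pooled z) or 4.3%, 4.7%, 4.95% (Fisher).

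**7. Stress case.** From 10 versus 1 infections of 100, two more on gentamicin alone give p = 0.045 (pooled z) or 0.082 (Fisher); three more give 0.096 or 0.164. With 20 lost per arm at the planned rates, the chance of two or more missed on gentamicin and none on saline is 0.0169 × 0.1216 = 0.002.

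**The case for a change.** The strongest case for a change is that it would be cheap. One sentence fixing the rule, an explicit entry for status not assessed, and a note that the power figure has no loss allowance would need no extra patients or visits. With about 11 events expected, a reader of a borderline result would like to know the rule was not picked afterwards. The outline records arm and infection side by side, and dates are easier to recover from the chart while records are still linked. All of that is fair, and the gap in the text is not in dispute.

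What does not stand is the step from gap to error. The Statistics sentence about analysis after tabulation defers only other analyses. It does not say that the primary rule would be chosen with arms in view, and Data and Safety Monitoring holds back all results until the last follow-up in order to reduce bias. The unknown status of early leavers is also less general than it looks. Inpatient monitoring and clinic visits allow repeated observation before 8 weeks, and the visit rows let an analyst see who missed a visit.

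Nor is there a clearly better rule to require. Rule B, the natural candidate, overstates the difference most. A Kaplan-Meier estimate meets a zero variance in the gentamicin arm whenever that arm has no infections (0.99^100 = 37% at the planned rate), and a simple Wald interval for the proportions has the same weakness. The choice is a trade-off.

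**Conclusion.** The concern does not call for a change. The plan leaves out a detail: who is in the denominator when follow-up is incomplete. An analyst can fill it sensibly by reading the endpoint as infection by 8 weeks, counting infections whenever recorded, stating how the rest were handled, and reporting their number by arm.

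No stated figure is shown to be wrong. The 80% power is correct by the two-sided pooled formula at 100 per group, and the documents contain no loss rate against which to fault it; at 5% loss the formula still gives 78.1%. Any single rule holds type I error near or below 5%. Choosing afterwards among all three would reach 6.3% to 7.6% by pooled z and stay within 5% by Fisher's test. The two rules that keep observed infections differ on significance in 2.1% to 4.0% of trials by pooled z, or about 4.0% to 5.1% by Fisher's test.

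These sizes rest on assumed losses of 10% to 30%, equal in both arms and unrelated to infection, with half of the lost patients' infections seen. Heavy loss, or loss that differed between arms, would matter more, but nothing in the documents points to either.
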